## Detailed Protocol: SAGE

skip over any questions that they choose not to answer. A subject may experience some tiredness or restlessness during the experimental tasks. If so, the subject can take a break or discontinue the testing.

Obtaining a blood sample by inserting a cannula into a vessel is a routine and safe procedure. However, complications can occur, such as bleeding, bruising, and feeling dizzy/lightheaded. There is a small risk of infection, and of fainting. Bloods will be drawn by experienced phlebotomists.

There are no serious risks associated with the collection of electrophysiological (ERP) data. The cap with electrodes fits snugly and may cause minor discomfort. If so, the investigator will try to adjust the fit. Different sized caps will be available to facilitate a comfortable fit. There is a small risk of minor skin sensitivity, chapping, or drying associated with the conductive gel. Also, there is a slight risk for infection at an electrode site, if the skin is injured during the procedure. The electrode gel itself may leave the hair untidy. However, it is water-soluble and will wash out easily. Electrodes around the eyes and behind the ears are attached with stickers and may cause slight discomfort upon removal.

There are no known serious risks associated with measuring blood flow using Transcranial Doppler (TCD) Ultrasound. The headband that holds the ultrasound camera may cause minor discomfort. The technician carrying out this study will be experienced and try to adjust the fit to make it as comfortable as possible. During the n-back task, a subject may experience some fatigue or restlessness. If so, the subject can take a break or discontinue the testing.

There are no known serious risks associated with measuring movements using accelerometry. The band around the waist that holds the device fits snugly and may be experienced by some as uncomfortable. If so, the band can be adjusted to make it more comfortable.

There are no known serious risks associated with measuring heart rate using the using the Polar device. The band around the chest that holds the device fits needs to fit snugly may be experienced by some as uncomfortable. If so, the band can be adjusted to make it more comfortable.

### **Potential Benefits**

Evidence to date would suggest that participating in cognitively or physically stimulating activities may promote brain health. However, there are no proven benefits to subjects who participate in this study. The results may benefit others by elucidating mechanisms that contribute to successful cognitive aging. These results may be useful in developing rational interventions aimed at preserving cognitive and functional status in older individuals

### **Monitoring and Quality Assurance**

The Principal Investigator and Co-Investigators will report any and all serious and non-serious adverse events to the IRB within a timely manner.

Study personnel must immediately report to the PI any adverse events from this study. All adverse events will be reviewed by the PI and reported to the Partners Human Research Committee (HRC) in accordance with ICH Guidelines.

The PI will be responsible for monitoring and assuring the validity and integrity of all of the data, for monitoring the day-to-day activities of all study procedures, and for the adherence to the IRB-approved protocol. The PI will maintain a tracking log to reflect all adverse events regardless of relationship or expectedness and submit the updated log each year during the IRB renewal process.

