### Interventions – General Features and Overview

All of the interventions will include the following features: the duration will be ~35 minutes per day, 5 days/week, over a 5 week period. A member of the research team will visit the subject's home to introduce the training program, and carefully review how to use the appropriate software on a computer, which will be loaned to subjects while they participate in the project. If the subject's home does not have internet access, the tablet provided will include prepaid wireless internet access. The team member will be present during a practice run to facilitate the process and address any concerns.

Subjects will be instructed to carry out the training sessions during the same part of the day (e.g., early morning), and to set up a routine in which they will not be disturbed by phone calls or visitors. Individuals will be told not train more than once a day. They will be encouraged to maintain their other activities and not substitute the training stimulation for another activity in which they have been routinely engaged.

For both cognitive and physical training, subjects will begin with a level they can easily manage. The difficulty will be slowly increased as their performance improves (due to training effects), with the aim of keeping the subjective effort approximately constant and moderately challenging through the 5 weeks. Similarly, for the mindfulness training, the meditations and tasks will become more self-directed and challenging during the 5 week course.

A member of the research team will communicate with each subject on a weekly basis (via phone call or email, whichever mode of communication is more convenient for the subject) to provide feedback and address any questions or concerns. Subjects will also be encouraged to contact the research team at any time they have questions or concerns. Data will be monitored for potential breaks, interruptions, and unusual performance fluctuations.

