## Detailed Protocol: SAGE

Aerobic exercises will include relatively low impact activities like walking, jogging, or running in place, which will aim to put limited demands on balance. Each exercise will be explained and demonstrated in the video. All exercises can be done standing, sitting, or next to a chair that provides balance support as demonstrated in the videos. After the first session, for each subsequent session the difficulty level will start at one level below the previous session's average difficulty level (e.g. if they exercise at the most difficult level for most of the time during one session, the next session will start at the medium difficulty level). Each exercise will be explained and demonstrated in the video.

There will be a water break every 8-10 minutes and an Exertion Check-In Break every 3-4 minutes. At each Exertion Check-In break, subjects will push one of 3 buttons to rate their perceived level of exertion ("Too Easy", "Somewhat Hard", "Too Hard"). If they choose "Too Easy", the next set of exercises will be a bit faster. If they choose "Too Hard", the next set of exercises will be a bit slower. If they choose "Somewhat Hard", the next set of exercises will stay at the same level. Subjects are told that the goal is to work at a level that requires a modest degree of effort, where they feel stimulated and like they are working hard, but not so hard that they feel dizzy or short of breath.

If they want to make the exercise easier or harder anytime, they can press the "Pause" button on the computer screen and choose "Too Easy" or "Too Hard".

If they would like a short break, they can also press the "Pause" button on the computer screen. When they are ready to start again, they can press the "Resume" button.

If they need to stop the exercise completely they can press the "Pause" button and then press "Start Over Later".

If, for some reason, they feel unable to carry out a particular exercise (e.g., inability to bend a knee because of arthritis), they will be able to press the "Pause" button and then the "Skip Exercise" button on the computer that will trigger the display and demonstration of an alternative exercise (e.g. Step Touch instead of Skipping).

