### **Risks and Discomforts**

During the Intervention Programs only subjects whose primary care doctor indicate are safe to engage in in the physical exercise training program will be able to participate in the study (even if they are randomly assigned to one of the non-physical exercise intervention programs). In the physical exercise training program, perceived level of effort will be carefully monitored and subjects who report their perceived exertion to be hard will be instructed to decrease their level of effort. During the initial visit to the subject's home, the study staff will prepare a card that includes the name and phone number of the subject's PCP, in case medical issues arise.

During all of the structured intervention phases, study staff will be regularly communicating with participants to answer questions, address concerns, and try to augment a subject's level of comfort with the training activity.

Physical fitness training for 35 minutes, titrated to a moderate level of effort, is generally safe and often recommended for healthy adults. During exercise, there is a risk of fatigue, dyspnea, palpitations, and muscle cramps or aches. Following exercise, there is a risk of muscle, joint, or back discomfort. While exercising, individuals with heart disease are at risk for chest discomfort/angina.

Subjects will be told that if they experience symptoms, they should stop exercising. If they experience chest discomfort, they should contact their primary care physician. If the chest discomfort is severe, 911 emergency medical services should be called and the subject should be taken to a hospital emergency room for evaluation. For other symptoms, they should page the research team.

The PI, a physician, will review the symptoms with the subject and help determine whether further medical assessment is appropriate. As a safety measure, subjects can only participate in this study if approved by their primary care physician.

Cognitive training poses no serious clinical risks for participants. The cognitive exercises may cause some degree of frustration or fatigue. The subject may stop the testing at any time or decline to answer any question.

Awareness training poses no serious clinical risks for participants. It may make some individuals feel fatigued or frustrated.

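### The protocol promises a log of all adverse events, but no arm is asked about them and only the exercise text tells subjects to report symptoms, so the log is likely to be incomplete and may be unequal by arm.

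*Protocol*

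**What the plan says.** **The promise.** Monitoring and Quality Assurance states: "The PI will maintain a tracking log to reflect all adverse events regardless of relationship or expectedness". The updated log goes to the IRB at each annual renewal. The route into the log runs through staff: "Study personnel must immediately report to the PI any adverse events from this study". Neither sentence is limited to one arm.

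**The exercise arm.** After listing the risks of physical training, Risks and Discomforts says "Subjects will be told that if they experience symptoms, they should stop exercising". It gives steps for chest discomfort and then adds "For other symptoms, they should page the research team". A review follows: "The PI, a physician, will review the symptoms with the subject and help determine whether further medical assessment is appropriate".

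**The other three arms.** The next paragraphs of the same section cover cognitive training, which includes the non-adaptive control, and mindfulness. They name fatigue and frustration as possible effects and otherwise reassure, for example "Awareness training poses no serious clinical risks for participants". They do not tell subjects to report symptoms to the team.

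**All arms.** Interventions – General Features and Overview provides a weekly phone call or email "to provide feedback and address any questions or concerns", and the individual arm descriptions repeat that purpose. Subjects are also encouraged to get in touch whenever they have a question or concern. Post-Intervention Assessment lists blood collection, cognitive tests, questionnaires, neurologic and gait assessment, ERP and Doppler studies. It lists no adverse event enquiry.

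**The concern.** A log that covers events whatever their cause or expectedness can be complete only if staff hear of events that subjects themselves do not connect with the training. Nothing in the protocol makes that happen. A fall, a dizzy spell or a clinic visit in someone doing computer or mindfulness sessions at home reaches the log only if the subject thinks to raise it.

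The instruction that would prompt such a report appears only in the exercise text. Two things are at stake:

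- **Oversight.** The investigator and the IRB would work from a record that is probably incomplete. Unexpected effects of the mindfulness and cognitive programs, and events unrelated to training, are the likeliest to be missed.
- **Reading by arm.** Subjects are 65 or older, so aches and fatigue are plausible in any arm. If the log is ever tabulated by arm, true risk and readiness to report cannot be told apart.

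**Working it through.** The protocol gives no adverse event rate, capture rate or safety sample size, so there is no stated figure to reproduce. The check is a comparison of the text, followed by an illustration on assumed values.

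**Step 1: each possible route into the log, by arm (protocol text only)**

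| Route | Exercise | Adaptive cognitive, mindfulness, control |
|---|---|---|
| Instruction to report symptoms to the team | Yes (Risks and Discomforts) | None found |
| Review of reported symptoms by the PI | Yes, after the subject reports | None described |
| Weekly call or email | Feedback, questions, concerns | Same |
| Open invitation to contact the team | Yes | Same |
| Scripted adverse event question, weekly | None | None |
| Adverse event enquiry after the intervention | None listed | None listed |
| In-session prompt | Effort rating only | None |

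The last row needs care. The exercise program has "an Exertion Check-In Break every 3-4 minutes", but the subject chooses among three effort ratings that set the pace of the next exercises. It does not ask about symptoms or events.

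**Step 2: what follows from the table.** No row shows staff asking any subject about adverse events, so capture is passive in all four arms. The arms differ in the first two rows: exercise subjects are explicitly told to report, and their reports are then reviewed.

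**Step 3: how a difference in capture would show in the log.** Let the true event rate be *p* in every arm, and let the probability that an event reaches the log be *c*E in exercise and *c*O in another arm. Then

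logged ratio = (*p* × *c*E) / (*p* × *c*O) = *c*E / *c*O.

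The true rate cancels, so no incidence has to be assumed. The capture probabilities below are assumptions:

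| *c*E | *c*O | Logged ratio | Events missed in the other arm |
|---|---|---|---|
| 0.90 | 0.90 | 0.90 / 0.90 = 1.0 | 1 − 0.90 = 10% |
| 0.90 | 0.50 | 0.90 / 0.50 = 1.8 | 1 − 0.50 = 50% |
| 0.90 | 0.45 | 0.90 / 0.45 = 2.0 | 1 − 0.45 = 55% |

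The range starts at 1.0 because the document does not show that capture differs at all. It shows only that the instructions do.

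**The case against.** The case on the other side has four parts.

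1. **Self-report in every arm.** A reader might infer that exercise events are actively solicited while the rest are merely volunteered. The text does not support that. Exercise subjects are told to page the team when they notice something, which is still self-report; the effort check asks nothing about symptoms; and staff contact has the same stated purpose in every arm. The contrast is between one arm with an explicit instruction and three without. This part stands in full.
2. **Shared routes.** Weekly contact covers concerns as well as feedback, everyone may call at any time, training data are watched for interruptions, and all subjects return for two half-day sessions with questionnaires and a neurologic and gait assessment. An illness or injury could surface by any of these. That makes capture outside the exercise arm passive rather than absent, but none of these routes asks about events.
3. **No planned comparison.** A reader might infer that the trial's results are biased, or that the active control fails as a background rate for safety. Neither follows. Specific Aims and Biostatistical Analysis contain no between-arm safety comparison, and the control is nowhere offered for that use. This part also stands, and it limits the consequence.
4. **Unseen consent forms.** Randomization implies forms that differ by condition, and they are not part of the text under review. They may tell other subjects to report problems, so the finding can be asserted of the protocol text only.

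A fuller symptom instruction for the one physically demanding program is also ordinary, risk-proportionate practice and is not itself an error. The gap is that the promise of a complete log has no matching collection step in any arm.

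**Conclusion.** The point holds in a limited form. The protocol commits to a log of every adverse event but provides no step for asking about them, and within its text the one instruction to report symptoms to the team is specific to exercise. The log is likely to be incomplete and may be unequal by arm.

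It would go too far to say that the log will be unequal. Neither the existence nor the size of a gap can be derived from the document, and the ratios of 1.0 to 2.0 rest on assumed capture probabilities and equal true rates. The planned efficacy analyses are not affected. The consequence is for safety oversight and for anyone who later reads the log by arm.

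How events are elicited is a matter of trial conduct. A statistical analysis plan could not recover events that nobody asked about, so this belongs in the protocol. It is a modest but worthwhile improvement.

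**What to change.** - **Interventions – General Features and Overview:** add to the existing weekly call or email, in all four arms, one identical, open and non-leading question about new symptoms, injuries, falls or medical visits since the last contact.
- **Post-Intervention Assessment:** add the same question to the list of measurements.
- **All arms:** give every subject the same instruction to notify the team of medical events, and check that the consent forms agree with it.
- **Monitoring and Quality Assurance:** record events by arm, each marked as solicited or spontaneous, and make clear that staff report events to the PI whatever their relationship to the study, so that this sentence matches the scope of the log.

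The exercise symptom instructions in Risks and Discomforts stay as they are.

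The cost is one scripted question in contacts that already take place. The downside is more minor events to log, with logged rates likely to rise most in the non-exercise arms.
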